The IVR system includes tailored scripting of Gout Flare and Patient Reported Outcome questions (with skip logic), recorded by a member of the research team. The system will automatically dial participants at a schedule time (eg. Monday 4 PM) and if no answer will attempt 2 more times at the same time over the following 2 days (eg. Tuesday 4 PM, Wednesday 4 PM). Participants will self-navigate through the questions using their telephone keypad. Participants can also call into the system to complete surveys if they experience a flare on a day they are not scheduled to receive a call. The IVR system will be programmed to call the patient weekly for 12 weeks to complete a weekly Gout Flare Survey. Consistent with the published gout flare self-report definition, gout flare ascertainment questions will include whether the recent flare is similar to past flares, the number of swollen joints and the number of warm joints. Pain at rest during the attack will be assessed on a 0-9 scale. Together, these questions attain 90% accuracy with physician-diagnosed gout. Further questions will include peak pain, timing of attack and duration of attack if completed. We will capture patient reported outcome measures (e.g. pain, fatigue, sleep) using instruments from the NIH PROMIS assessment center (<https://www.assessmentcenter.net/>). In addition IVR questionnaires at months 1, 3, and 6 will assess IVR ease of use, burden of use, willingness to continue use and disruption to daily activities. At enrollment the study coordinator will explain how the IVR works, planned survey schedule, and that participant -initiated calls to IVR are allowed.

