Participants randomized in Phase 1 to the RheumPRO application will complete the exact same Gout Flare Survey questions as the participants randomized to the IVR group, but will complete them using the RheumPRO application that will be downloaded on their smartphone. The RheumPRO application will be programmed to notify participants weekly for 26 12 weeks via a scheduled (eg. Monday 4 PM) “pop-up” to complete Gout Flare and Patient Reported Outcomes Surveys. Participants self-navigate through the survey questions using their smartphone. If participants do not complete the Gout Flare RheumPRO will generate 2 more “pop-ups” at the same time over the following 2 days (eg. Tuesday 4 PM, Wednesday 4 PM). Participants can also open the RheumPRO application on their smartphone and complete surveys or if they experience a flare on a day they are not scheduled to complete a survey. In addition, RheumPRO questionnaires at months 1, 3, and 6 will assess RheumPRO ease of use, burden of use, willingness to continue use and disruption to daily activities. At enrollment the study coordinator will explain how RheumPRO works, planned survey schedule, and that participant -initiated surveys in RheumPRO are allowed.

Phase 2:

At the conclusion of 12 weeks individuals will “crossover” to the opposite study arm and will continue in the study for an additional 12 weeks using the opposite technology to report their flare frequency/intensity (i.e., those randomized to IVR for the first phase will use the RheumPRO app in the second phase and vice-versa) completing the exact same Gout Flare and Patient Reported Outcome questions as were completed in Phase 1. Activities to be completed at each study visit are detailed below.

Figure 1. Study Workflow

[figure not shown]

Table 1. Study Visits and Evaluation

[figure not shown]
	1	2	3	4	5	6	7	8	9	10	11	12	13	14	15	16	17	18	19	20	21	22	23	24	
Informed Consent	X																								
Paper Screening	X																								
Paper Enrollment	X																								
IVR/RheumPRO Initial Flare Assessment	X																								
Patient- Weekly Flare Assessment*		X	X	X	X	X	X	X	X	X	X	X	X	X	X	X	X	X	X	X	X	X	X	X	X
2 week adherence call		X																							
1-month follow-up Assessment and phone check-in				X																					
3-month follow-up Assessment												X													
Crossover Study Visit†													X												
1-month follow-up Assessment and phone check-in																		X							

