6-Month follow-up Assessment																									X
Unscheduled Patient Initiated Flare Assessment																									

*Weekly flare assessment are completed by patient using IVR or RheumPRO application; †Crossover visit will be conducted in person at the study site.

[figure not shown]

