10.2.3.2 New IVR Participant

Before crossing over participants to the IVR, the participant will need to have the RheumPRO app uninstalled from their smart phone. To uninstall app: hold down on the desired app to uninstall. Once the app begins to shake, tap the x in the top left corner to delete the app from the phone

- First uninstall the RheumPRO app by holding down on the app until it starts to wiggle. Tap the "X" in the top left corner and confirm deletion.

- After uninstalling of RheumPRO app, patient will need to log-on to website to register with IVR system
- Website to log-in: secure.aging.uab.edu
 - Password: **[name]**

Division of Gerontology, Geriatrics, and Palliative Care Logon Page

[figure not shown]
This page is used to access documents.

Palliative Care Resident Library

Study of Aging

Gout Pro Study

- Once password has been entered on website, please have the following information ready
 - Study ID
 - Patient preferred phone number
 - Preferred Call Time

This page is for data entry. 

Subject ID:
Subject phone number:
Preferred call time (Format military time HH:MM):

- Immediately after entering information into webpage a call will need to be placed to IVR system
 - **[contact])**
- Enter study ID using keypad into IVR
- Record patients name, using their own voice and complete first flare assessment using touch-tone keypad on smart phone
- Make sure the coordinator writes down the preferred call time for IVR system and preferred phone number for future calls
- Remind participant of IVR call schedule.
 - Will be conducted weekly throughout the study period
 - Participant will designate a time for phone calls to be made
 - Confirm preferred phone number for IVR calls

- Provide participant with reminder card and trouble-shooting pamphlet
 - Card will have study ID and phone number
 - Remind participant that study ID will be entered into IVR to confirm participation
- At the end of the visit, the coordinator will need to send enrollment form, consent form, W9, and preferred phone number, and call time to UAB
 - Send all forms the same day to [contact]

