12.1.8 Incomplete or Illegible forms

If any section or an entire page of the forms cannot be completed (e.g., no parts have any responses), and it is unlikely that it will be completed, indicate NOT DONE/ND, NOT AVAILABLE/NA or NOT APPLICABLE/NAP, as appropriate. Do not leave forms incomplete or unused without explanation.

All form header information must be completed even though no data are recorded on the electronic form. If an electronic form can only be partially completed at the time of visit, but will be completed when the information becomes available, note this in the MISSING FORMS / INCOMPLETE FORMS field and follow the direction of the study coordinator and principal investigator.

13 Analysis Plan

Since the study is a pilot study to demonstrate feasibility of recruiting and training gout patients to utilize RheumPRO and IVR, a priori sample size calculations were not performed. We will summarize baseline characteristics of study participants as means with standard deviation (SD) for continuous and ordinal measures and number and percentage for categorical variables. All statistical analyses followed standard methods for a 2-by-2 crossover design. Preference and satisfaction surveys will use dichotomous questions and/or a Likert scale (range 0 to 10; very easy to very difficult). Differences between the RheumPRO and IVR approach will be evaluated using McNemar's test for dichotomous variables, paired t test for continuous variables, and nonparametric Wilcoxon signed rank test for ordinal variables. Qualitative questionnaire data for lack of response will be summarized as percentages. We will conduct sensitivity analyses with multiple imputations to examine the robustness of the reported results and the effects of missing data for both the as-treated and intent-to-treat populations. A two-sided alpha of 0.05 will be used to determine significance.

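### The 3-month and 6-month usability ratings appear to be taken through the mode being rated, with no other route written for people who have stopped answering it

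*Combined protocol and SAP*

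**What the plan says.** Section 10.1 places the usability items in questionnaires named after each mode: "IVR questionnaires at months 1, 3, and 6 will assess IVR ease of use, burden of use, willingness to continue use" and "RheumPRO questionnaires at months 1, 3, and 6 will assess RheumPRO ease of use, burden of use, willingness to continue use". Both sentences go on to add disruption of daily life.

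Table 1 puts the 3-month assessment at visit 12 and the 6-month assessment in the last column. Section 10.2.2 has participants complete visits 2 to 12 themselves in IVR or RheumPRO, and Section 10.2.4 describes visits 14 to 26 in similar terms. Staff contact by telephone is tied to the two rows labelled "1-month follow-up Assessment and phone check-in", not to the 3-month or 6-month rows.

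Visit 13 is face to face: "Crossover visit will be conducted in person at the study site". Its steps in Section 10.2.3 cover installation, registration and a first flare assessment in the new mode. None obtains a rating of the outgoing mode. For people leaving RheumPRO, Section 10.2.3.2 says "Before crossing over participants to the IVR, the participant will need to have the RheumPRO app uninstalled from their smart phone". No equivalent removal step is written for people leaving IVR. For them, Section 10.1 says only that "The IVR system will be programmed to call the patient weekly for 12 weeks to complete a weekly Gout Flare Survey".

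Section 13 compares the modes with McNemar's test, the paired t test and the Wilcoxon signed rank test, and uses multiple imputation as a sensitivity analysis. It also says "Qualitative questionnaire data for lack of response will be summarized as percentages", without saying when or by what route those data are collected.

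**The concern.** Acceptability is a main product of this feasibility pilot, and the people who give up on a mode are those whose opinion of it matters most. If the request for a rating arrives through the mode they no longer answer, many will not give one. Each planned test needs both ratings from the same person, so one missing rating removes that person from the comparison.

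Where stopping is linked to difficulty, the remaining raters are the more satisfied ones. The mode with more stopping then looks better than it is. If that is the harder mode, the contrast is diluted. Multiple imputation in its standard form assumes that missingness is explained by the observed data, which is doubtful when the unobserved opinion is the reason for the missing value. Section 13 names no imputation model and no missing-not-at-random scenario.

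**Working it through.** The plan states no stopping rate, expected rating, standard deviation or bias figure, so there is nothing of its own to reproduce. What follows shows direction and plausible scale only.

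**Inputs from the documents.** Ratings run from 0 (very easy) to 10 (very difficult), comparisons are paired and alpha is 0.05 two-sided (Section 13). The number of participants is taken as 45, the number of Fitbits supplied (Section 8); no sample size was calculated.

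**Simple arithmetic (all rates assumed).** Suppose stoppers would score a mode 3 points harder than responders. Responders' mean then understates the true mean by 3 x p, where p is the stopping rate. The between-mode difference shifts by 3 x (pA - pB) in favour of the mode with more stopping:
- 30% against 10%: 3 x 0.20 = 0.6 points
- 20% against 10%: 3 x 0.10 = 0.3 points
- equal rates: 0

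If 90% of responders are willing to continue and no stopper is, true willingness is 0.9 x (1 - p): 81%, 72% and 63% at 10%, 20% and 30% stopping. This calculation treats a person's two modes as independent, which is doubtful in a crossover.

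**Simulation with correlated ratings (assumed inputs).** Difficulty of the two modes is bivariate normal with means 3 and 4, or 3 and 5, SD 2.5 and correlation 0.3, truncated to 0-10. The chance of no rating for a mode is 1/(1 + exp(-(b + s(x - 4)))), where x is that mode's own difficulty. Power is the normal approximation Phi(|mean d|/(SD d/sqrt(n)) - 1.96), where n is the number of complete pairs. The last column assumes that a catch-up by another route recovers 80% of missing ratings.

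| True difference | b, s | Missing, easier / harder mode | Difference in complete pairs | Pairs of 45 | Power | After catch-up: difference (pairs) |
|---|---|---|---|---|---|---|
| 0.91 | -1.5, 0 | 18% / 18% | 0.92 | 30 | 0.45 | 0.92 (42) |
| 0.91 | -2.2, 0.25 | 9% / 11% | 0.89 | 36 | 0.51 | 0.91 (43) |
| 0.91 | -1.5, 0.25 | 17% / 20% | 0.86 | 30 | 0.43 | 0.90 (42) |
| 0.91 | -1.5, 0.5 | 17% / 24% | 0.78 | 29 | 0.38 | 0.89 (41) |
| 0.91 | -0.8, 0.5 | 27% / 35% | 0.74 | 22 | 0.29 | 0.89 (40) |
| 1.86 | -1.5, 0 | 18% / 18% | 1.86 | 30 | 0.96 | 1.86 (42) |
| 1.87 | -2.2, 0.25 | 9% / 14% | 1.81 | 35 | 0.98 | 1.86 (43) |
| 1.86 | -1.5, 0.25 | 17% / 24% | 1.78 | 29 | 0.94 | 1.85 (41) |
| 1.86 | -1.5, 0.5 | 17% / 32% | 1.61 | 26 | 0.89 | 1.83 (41) |
| 1.86 | -0.8, 0.5 | 27% / 44% | 1.53 | 19 | 0.76 | 1.84 (39) |

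With all 45 pairs, power is about 0.60 for the smaller gap and 0.99 for the larger. With s = 0 there is no bias, only loss of pairs: 45 x 0.82 x 0.82 = 30. With s above 0 the difference shrinks by about 2% (1 - 0.89/0.91) to 19% (1 - 0.74/0.91).

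**The case against.** The route of the usability questionnaires is never stated outright. Their names could mean questionnaires about a mode. The Table 1 footnote on completion through IVR or RheumPRO marks only the weekly flare row. Section 13 also mentions preference and satisfaction surveys, which need not sit inside either mode. A reader might infer that ratings are collected only through the mode being rated, but no sentence says so. What stands is the natural reading: Sections 10.2.2 and 10.2.4 have the participant complete those visits in the mode, and no other route is written for the 3-month or 6-month rating.

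Two further inferences go too far. One is that the first mode is removed at visit 13, which is written for RheumPRO but not for IVR. The other is that deleting the app makes the rating unrecoverable; staff can still ask the questions.

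There is also real mitigation. Someone who stops late may already have a 1-month rating, and Section 13 does not say which time point is compared. Section 5.2 provides weekly monitoring of the flare surveys, so stoppers should be noticed. Reasons for lack of response are to be summarised. These measures reduce the problem, but none of them is a step to collect a missed rating. A 1-month rating may also predate the experience that made the person stop.

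Finally, this is a pilot without a sample size calculation. That lowers the stakes of a p-value, but not the need for a fair picture of acceptability.

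**Conclusion.** The point holds as a conditional one, with moderate confidence. As written, the end-of-phase ratings appear to depend on the mode being rated, and no catch-up is planned at visit 13 or at the end of phase 2. The bias requires both that non-response is linked to difficulty and that one mode loses more people than the other. The mode with more stopping is then flattered, and if it is the harder mode the between-mode difference is attenuated. Pairs are lost whatever the cause of non-response.

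The size cannot be derived from the documents; the attenuation of about 2% to 19% and the 19 to 36 remaining pairs rest on the assumed inputs above.

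A reader might infer that the poorer mode would come out ahead. The documents do not support that: they give no rates or ratings from which it could follow, and the order of the modes did not reverse in any simulated scenario.

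**What to change.** - **Section 10.2.3:** make it the first step of visit 13, before any uninstall or new registration, that every participant who lacks a 3-month rating of the first mode completes it on a short paper form.
- **Section 10.1 and Table 1:** have the coordinator obtain the end-of-phase-2 rating by telephone from anyone who has not given it. State the route of all usability questionnaires. Reconcile months 1, 3 and 6 for each mode with two 12-week phases, since month 6 can apply only to the second mode.
- **Both contacts, and any withdrawal:** ask non-responders why they did not respond to that mode.
- **Section 13:** name the end-of-phase rating of each mode as the one used in the paired comparison, record the route of collection, and repeat the comparison with in-mode ratings only.

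The cost is one short form at a visit already held in person and a few calls by existing coordinators. The downside is that some ratings will be taken on paper or by staff, so route is linked to non-response. Recording the route and repeating the comparison shows how far this matters but does not remove it.

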10.2 Participant Evaluations- Study timeline, visits, and procedures

10.2.1 Visit 1

[figure not shown]
- Identify eligible patients through medical record review, clinical referral
- Research coordinator will call potential participants based on inclusion criteria.
- If participant agrees to participate complete screening form and depending on urate level and last lab values, may need to get new lab values before enrollment.
- If lab values need to be collected before study inclusion, ask patient to arrive 1 hour early to have new labs recorded
- Once lab values are available determine eligibility
 - IF NOT eligible, thank participant for their time and place screening form in binder
 - If participant is eligible, they will need to complete an enrollment form, consent form and W9 for the study
 1. Confirm smart phone is up to date on operating system (iOS 8 and up and android 4 (Jellybean and up)
 2. Confirm phone enough memory to download Fitbit app
 - iPhone
 - To check available memory open the settings app and under the general tab there is a tab labeled storage and iCloud usage.
 - The available storage will be listed, and if changes need to be made they can be addressed under “manage storage”

[figure not shown]
- Android
 - To check available memory open the settings app and open the storage tab to find the available storage
 - If changes need to be made apps or text messages can be deleted

[figure not shown]
- Place screening form, enrollment form, consent form, and W9 in study binder
- Please be sure that the participant has entered a valid phone number and an email address
 1. Place test call to phone number provided to make sure it is valid
 2. Review email address to ensure it is valid (eg. [contact]), and it is legible
- Pull randomization assignment from study binder and add study ID to screening and enrollment form
- Begin Fitbit for smart phone installation (Be sure to write Fitbit serial number (located on bottom of box) in the enrollment log page in study binder
 - Turn on Bluetooth and ensure location is turned on
 1. Open the settings app and turn on Bluetooth

[figure not shown]
- Download Fitbit app from apple store or Google play store
 1. If memory full, ask participant what can be deleted to accommodate the app
 2. If participant doesn't want to delete, they are not eligible for the study
- You will be prompted to create an account. Please press "Join Fitbit"

[figure not shown]
- Select the Charge HR model

[figure not shown]
- Continue through the prompts "Set Up Your Fitbit Charge HR"

- Enter participant height, gender, weight, and birthdate
- The next screen will require the participants full name, email and password.
 1. They will need to agree to the terms of use, and uncheck the option to receive updates about Fitbit products, news, and promotions.
 2. Confirm email address matches email on consent form. If not please make a note

- On the next screen they will need to agree once again to the terms of service by tapping “next”
- Next a 4-digit number will be displayed on the Fitbit and the number will need to be entered into the app. **Make sure other Fitbits are out of range to avoid a sync issue.**

- The participant is now ready to use the Fitbit
- **Don't forget to document Fitbit serial number (located on bottom of box) in the screening log**
- Double check the app has been installed and double check the phone and Fitbit are able to sync properly
- Review how to charge Fitbit, (proper use of the Fitbit charging cable)

10.2.1.1 RheumPRO Arm

[figure not shown]
- RheumPRO app installation
 - Coordinator will type in web address to access RheumPRO application
 1. Web Address <https://dev-rheumpro.hs.uab.edu/goutpro/>
 - Once participant accesses the link via their smart phone, identify the operating system, either iPhone or Android
 - There is a possibility of connectivity issues with the RheumPRO app
 1. for Android Users it will prompt the download of the APK which they can then install.
 2. There have been documented issues opening the app and using the features while on the UAB Wi-Fi.
 3. If you are unable to connect try another Wi-Fi network
 4. If unsuccessful try downloading the app or reloading app page using cellular data

- After password is entered, a page description of the app, click on “install application will be seen, and a pop-up window will appear to confirm installation

- Once the install application button has been selected, there are a series of direction on the screen prompting the participant to be sure the installation has proceeded. Helpful pointers are listed below:
 1. “in progress”:
 - Installation will be performed in the background (since iOS7): check the icons on device’s home screen
 2. “or not”
 - If the iOS popup “Would you like to install...” did not appear, check that participant doesn’t already have the same app installed from the AppStore
 - If an app with the same bundle identifier is already installed on the device from the AppStore, nothing will happen
 - Delete the app installed from the AppStore to be able to install this one
 3. “Nothing seems to happen”
 - After tapping the “install” button in the popup, if nothing seems to happen and participant is still on the same page, check device home screen: the installation should be in progress: should see the icon of the app somewhere and a progress bar
 4. “Unable to download app popup”
 - First check internet connection, and be sure that device is not behind a firewall that may prevent downloading .ipa files
 - Most common installation issues are:
 - Expired provisioning profile
 - Incompatible device (check iOS version, device family, and required device capabilities)
 5. If a popup with “untrusted enterprise developer” is displayed.

- Direct participant to settings -> General-> Device Management-> Click on appropriate Enterprise App (University of Alabama at Birmingham and click trust
 - Add layout for android
6. Now go back to homepage and click on app
 7. Popup window will be displayed when app is opened requesting “DevRheumPRO would like to send you notifications, press “OK”

8. If new to RheumPRO click on register
9. The app will prompt you to reference the physical consent document for the study. It will ask you to press next
10. The next screen will ask the participant to answer whether they have signed the physical consent document
11. If they have, press agree and a new screen will ask them to sign with their finger and type in their name and submit

12. The next several screens require the participant to create an account. They will need to provide (the questions are spread out over 4 separate screens):

- Email address
- Password
- First/Last Name
- Relationship to Arthritis: Patient, Caregiver, etc.
- Sex
- Race
- Date of Birth
- Country
- Zip Code

Step 2 of 4

First Name:

Last Name:

Relationship to Arthritis:

Sex:
 Male
 Female

Race:

Hispanic:

Date of Birth:

Twitter Handle: Optional

- Twitter Handle is not a required field**

Step 3 of 4

Country:
 United States of America

Postal Code:
 00000

A valid zipcode is required

Filling in the optional fields below may help us personalize your news, research opportunities and link your account to other services more efficiently in the future.

State: Optional
 Select State

City: Optional
 City

Address Line 1: Optional
 Street/PO Box/etc

Address Line 2: Optional
 Apt/Suite/etc

Previous Next

- Postal Code/Zip is required; address is not **

Step 4 of 4

Select diseases that you have been diagnosed with:

Ankylosing Spondylitis
 Dermatomyositis
 Fibromyalgia
 Gout
 Inflammatory Bowel Disease
 Juvenile Idiopathic Arthritis
 Lupus
 Osteoarthritis (degenerative arthritis)
 Osteoporosis/Osteopenia/low bone mineral density
 Polymyositis
 Psoriasis
 Psoriatic Arthritis
 Rheumatoid Arthritis
 Scleroderma (systemic sclerosis)

Select Insurance

[figure not shown]
Medicare
 Medicare Advantage
 Medicaid
 Tri-care / Military
 Commercial/Private insurance
 Other type of insurance
 No insurance

I Have a Rheumatologist

[figure not shown]
Previous Submit

- There is no need to click on the “I have a rheumatologist” button. It is not necessary for the app registration**

13. Upon completion of registration the app homepage will be displayed. In order to give permission for RheumPRO to access the Fitbit data, click on “Health Devices”

14. An icon with “Fitbit” and a “+” will be displayed.
15. Click on the “+” to add the participants Fitbit.
16. A log-in page will be displayed and the participant will need to add their Fitbit login credentials
17. A new page will be displayed asking for permission to access the Fitbit data. We want to have access to all 4 fields. Press Allow to complete authorization

18. The next page will be a confirmation screen, and hit done in the bottom left corner to return to the home page.
19. The initial flare assessment should be available to complete. Please make sure the participant completes this survey before leaving

- Provide participant with reminder and trouble-shooting pamphlet.
 - Don’t forget to fill in study ID, RheumPRO account information, and Fitbit account information.

